8 STUDY FLOWCHART

Study Phase	Screening ^a	Double-Blind Treatment Phase						Follow-up Phase	
		Day 1	Day 2	Day 3 (ECR 48- 72 hr after first dose)	Day 7	Day 10 ^c	EOT ^d	PTE ^e	Final Follow-up ^f Day 30-37
Signed Informed Consent ^g	X								
Demographics	X								
Medical/surgical history and current medical conditions	X								
Prior and concomitant medications ^h	X	X-----X							
Clinical assessment of the site of infection ⁱ	X	X	X	X	X	X	X	X	X
Assessment of lesion size ^j	X	X	X	X	X	X	X	X	X
Diagnosis of ABSSSI and photograph of the lesion site ^k	X								
Numerical Rating Scale for pain at the primary lesion site	X			X			X		X
SF-36v2 [®] Health Survey	X								X
Physical examination ^l	X						X		X
Vital signs									
Respiratory rate	X	X	X	X	X	X	X	X	X
Body temperature	X	X	X	X	X	X	X	X	X
Blood pressure	X	X ^m	X ⁿ	X ⁿ	X	X	X	X	X
Pulse/heart rate	X	X ^m	X ⁿ	X ⁿ	X	X	X	X	X
12-lead ECG ^o	X						X		
Urine dipstick test ^p	X								
Local urine or serum pregnancy test ^q	X								
Central serum pregnancy test ^r	X						X		X
Hematology ^s	X ^t			X	X	X	X		X
Serum chemistry ^s	X ^t			X	X	X	X		X
Blood culture ^u	X	As Clinically Indicated						X ^v	X ^v

Study Phase	Screening ^a	Double-Blind Treatment Phase						Follow-up Phase	
		Day 1	Day 2	Day 3 (ECR 48- 72 hr after first dose)	Day 7	Day 10 ^c	EOT ^d	PTE ^e	Final Follow-up ^f Day 30-37
Culture of infection site & Gram stain	X	As Clinically Indicated						X ^v	X ^v
Adverse Events ^w	X	X-----X							
Review of Inclusion and Exclusion Criteria/Randomization (if Eligible)	X								
Test Article Administration and Accountability ^x		X ^y	X ^z	X ^{aa}	X	X			
Plasma samples (in heparin) for PK analyses ^{bb}			X	X					
Assessment of need to continue therapy ^{cc}					X	X			
Investigator's Assessment of Clinical Response							X	X	

ABSSI = Acute Bacterial Skin and Skin Structure infection; AE = adverse event; β-hCG = beta – human Chorionic Gonadotropin; ECG = electrocardiogram; ECR = Early Clinical Response; eCRF = electronic case report form; EOT = end of treatment; ICF = informed consent form; PK = pharmacokinetics; PTE = post therapy evaluation; SAE = serious adverse event.

- ^a Following the signing of an ICF, all Screening evaluations, with the exception of the blood culture sample collection, should be completed within the 24 hours prior to randomization. The blood culture sample collection should be completed within 24 hours prior to the first dose of test article.
- ^b Day 1 is the first day of test article administration. Subsequent study days are consecutive calendar days.
- ^c A Day 10 visit should be conducted for subjects with treatment extending beyond 9 days, unless this visit coincides with the EOT visit.
- ^d To be conducted on the calendar day of, or within 2 days following the last dose of test article. Should also be conducted for any subject who withdraws prematurely or terminates participation in the study before completion.
- ^e To be conducted 7 to 14 days after the subject's last day of study therapy.
- ^f To be conducted 30 to 37 days after the first dose of test article. The Final Follow-up assessment may be conducted via telephone contact or by another interactive technology for subjects who were considered to be Clinical Successes and had no AEs or clinically significant laboratory or ECG abnormalities noted at or after the PTE visit. Otherwise, the visit must be conducted in person.
- ^g Written and signed ICF must be obtained before any assessment is performed.
- ^h Treatments that have been administered within the 7 days prior to the date of signing the ICF or during the Screening phase will be recorded in the eCRF. All medications and significant non-drug therapies (including physical therapy and blood transfusions) administered after the first dose of test article must be recorded in the eCRF.
- ⁱ Semi-quantitative description of infection features. Must be assessed within 48 to 72 hours after the first dose.
- ^j Measurement of the subject's lesion by ruler length × width. The Screening measurement must be collected within 4 hours prior to randomization. A lesion measurement must be completed within 48 to 72 hours after the first dose.
- ^k Diagnosis of the type of ABSSI (wound infection, cellulitis/erysipelas or major abscess) and anatomical location. A digital photograph of the infection site will be taken at Screening only.
- ^l A full physical examination will be completed at Screening; thereafter only changes from Screening measurements should be recorded as AEs in the eCRFs.

- ^m Blood pressure and pulse rate should be measured within 30 min before, and approximately (\pm 15 minutes) 1 hour after and 3 hours after the completion of the first dose on Day 1.
- ⁿ Blood pressure and pulse rate should be measured within 30 min before, and approximately (\pm 15 minutes) 1 hour after and 3 hours after the completion of the odd numbered doses on Days 2 and 3. In the event that the subject takes the dose before arriving for the office visit, the site should collect the 1 and 3 hour post dose measurements if possible, if not then a single measurement should be made at any time during the visit and the date and time recorded.
- ^o A 12-lead ECG should be performed at screening, at the EOT visit, and as otherwise clinically indicated.
- ^p A urine dipstick test will be performed locally at Screening.
- ^q All women will have a local urine or serum pregnancy test at Screening.
- ^r All women will have blood collected for a serum β -hCG pregnancy test at the Central Laboratory at the Screening, EOT and PTE visits.
- ^s Blood will be collected for hematology (includes coagulation) and serum chemistry testing at the Central Laboratory at Screening and at the Day 3, Day 7, Day 10, EOT and PTE visits.
- ^t At the Screening visit, blood will be collected for local laboratory hematology and serum chemistry evaluations required for assessing subject eligibility.
- ^u If bacteria are isolated from blood cultures, repeat blood cultures should be collected. If subsequent blood cultures are also positive, repeat the blood cultures as necessary until negative blood cultures are obtained.
- ^v At the EOT and/or PTE visit, blood cultures and infection site specimen cultures and Gram stains should be obtained only for subjects who are clinical failures and require alternative antibacterial treatment for the infection under study.
- ^w A subject's AEs and SAEs will be recorded and reported from signing of the ICF to the Final Follow-up assessment.
- ^x A 6 hour fast is required before and a 2 hour fast is required following all odd numbered doses. The total duration of test article therapy for all subjects will be 7 to 14 days. Test article may be dispensed and reconciled by blinded personnel. Subjects will be asked to return all unused test article and packaging at each visit. At the EOT visit subjects will return the test article packaging and site staff will perform accountability.
- ^y Subjects should receive their first dose of test article at the site within 4 hours after randomization.
- ^z Subjects should be instructed not to take the odd numbered dose on Day 2 until they return to the site for the Day 2 visit.
- ^{aa} Subjects should be instructed not to take the odd numbered dose on Day 3 until they return to the site for the Day 3 visit.
- ^{bb} At selected sites, subjects who have agreed to participate in PK evaluation and have signed a separate PK evaluation consent form will have up to 4 blood samples collected between Days 2 and 3. The PK sample collection schedule for the individual subject will be provided by the Sponsor.
- ^{cc} At the investigator's discretion, all therapy may be discontinued after the 7th day of treatment, when the infection is considered clinically cured (based on normalization of the clinical signs and symptoms of infection and the investigator's clinical assessment that continued systemic antibacterial therapy is no longer needed).

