14.1 Visit Schedule and Assessments

Refer to [Section 8](#), for the study procedures and their time points. There are 3 protocol-defined phases of the study: Screening, Double-Blind Treatment, and Follow-up. The study will have the following protocol-defined evaluations:

- Day 1 visit
- Day 2 visit
- Day 3 visit (Early Clinical Response [ECR] must be conducted between 48 to 72 hours after the first dose of test article)
- Day 7 visit
- Day 10 visit (A Day 10 visit should be conducted for subjects with treatment extending beyond 9 days, unless this visit coincides with the End of Treatment visit)
- End of Treatment (EOT): to be conducted on the calendar day of, or within 2 days following the last dose of any test article. If a subject withdraws prematurely or terminates participation in the study before completion, the EOT visit should be conducted
- Post Therapy Evaluation (PTE): to be performed 7 to 14 days after the subject's last day of study therapy
- Final Follow-up assessment: Day 30 to 37 (after the first dose of test article)

Subjects who discontinue study treatment prematurely should have the EOT visit and the procedures listed in Section 8, a PTE visit and a Final Follow-up assessment, if possible. The site should also collect subject safety information through the Final Follow-up assessment.

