14.3.1.1 Treatment Phase

The study will employ a double-blind, double-dummy design using omadacycline placebo comparator tablets of matching size and shape to active omadacycline tablets and matching over-encapsulated placebo and over-encapsulated active linezolid tablets. To maintain investigator and subject blinding, subjects on both arms will receive the same number of tablets as shown in [Table 1](#).

All doses of test article should be taken with water. There are fasting requirements for administration of the odd numbered doses due to effects of food on oral omadacycline (see [Table 1](#)). These fasting requirements should be considered when determining the time of day when subjects will take their doses.

In order to perform protocol-required procedures, Dose 1 and the odd numbered doses on Days 2 and 3 should be taken at the site. Ability to perform the study procedures and the fasting requirements for the odd numbered doses should be considered when determining when subjects visit the clinic on Days 2 and 3.

On Day 1, Dose 1 will be administered after the completion of all required Screening and Day 1 procedures and within 4 hours after randomization as outlined in [Section 8](#). On Day 1, a second dose should be taken provided that 1) it can occur a minimum of 8 hours after Dose 1, and 2) it can occur a minimum of 8 hours before the expected time of the next dose (ie, Dose 3); otherwise only Dose 1 should be taken that day. Starting on Day 2, test article will be taken twice daily, with approximately 12 hours (at least 8 hours) separating each dose.

Table 1. Treatment Regimens for Oral Test Article

Dosing		Omadacycline Arm	Linezolid Arm	Dosing Condition
Day 1	Dose 1	Three 150 mg omadacycline tablets and one over-encapsulated placebo tablet resembling linezolid	Three placebo tablets resembling omadacycline and one over-encapsulated 600 mg linezolid tablet	Fasting ^a
	Dose 2 ^b	One over-encapsulated placebo tablet resembling linezolid	One over-encapsulated 600 mg linezolid tablet	No restrictions
Day 2	Dose 3	Three 150 mg omadacycline tablets and one over-encapsulated placebo tablet resembling linezolid	Three placebo tablets resembling omadacycline and one over-encapsulated 600 mg linezolid tablet	Fasting ^a
	Dose 4	One over-encapsulated placebo tablet resembling linezolid	One over-encapsulated 600 mg linezolid tablet	No restrictions

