14.3.2 Permitted Dose Adjustments and Interruptions of Test Article

None.

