5.2 Efficacy Measures

5.2.1 Primary Efficacy Outcome

The primary outcome measure is Early Clinical Response at 48 to 72 hours (defined 46 hours to < 73 hours) after the first dose of test article in the mITT population. If more than one assessment of lesion size is done in the 46 to 72 hour time window, the latest will be used.

The primary outcome will be determined programmatically based on data recorded on the eCRF as follows:

Clinical Success will be defined as meeting all 3 of the following:

- The subject is alive
- The size of the primary lesion has been reduced $\geq 20\%$ compared to Screening measurements, without receiving any rescue antibacterial therapy
- The subject does not meet any criteria for Clinical Failure or Indeterminate (see below for definitions)

Clinical Failure will be defined as meeting any of the criteria below:

- The size of the primary lesion has not been reduced by $\geq 20\%$ compared to Screening measurements
- Investigator discontinued test article and indicated that the infection had responded inadequately such that alternative (rescue) antibacterial therapy was needed
- The subject received antibacterial therapy that may be effective for the infection under study for a different infection from the one under study up through the assessment of Early Clinical Response (ie, lesion size) or if no assessment was done in the 46 to 72 hour time window, up through 72 hours after the first dose of test article.
- The subject developed an AE that required discontinuation of test article prior to the Early Clinical Response assessment and alternative (rescue) antibacterial therapy was needed or if no assessment was done in the 46 to 72 hour time window, up through 72 hours after the first dose of test article.
- Death prior to Early Clinical Response assessment or if no assessment of Early Clinical Response (ie, lesion size) was done in the 46 to 72 hour time window, up to 72 hours after the first dose of test article.

Indeterminate The clinical response to test article could not be adequately inferred because:

- Subject was not seen for Early Clinical Response assessment because they withdrew consent, were lost to follow-up, or other specified reason
- Other specified reason

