8.6 Visit Windows/Unscheduled Visits

For the primary efficacy outcome, if more than one assessment of the lesion size is done in the 46-72 hour window, the latest will be used. For secondary and additional efficacy outcomes, the data collected at the EOT and PTE Visits, regardless of when these occur will be utilized in the analysis in the mITT population. The CE and ME populations exclude subjects with a visit occurring outside the window allowed per protocol.

For each safety outcome, analyses will utilize assessments occurring during the scheduled visit windows (provided in [Table 7](#)). Thus, if a subject has a visit outside the scheduled visit window, for example, a PTE Visit occurred 20 days after the subject's last day of therapy, the assessment will not be summarized with the PTE Visit but will be considered an unscheduled assessment. If a subject does not have an assessment at a scheduled visit and an unscheduled assessment was taken within the window for the time point (for example, 7 to 14 days after the subject's last day of therapy for PTE), these assessments will be summarized in the by time point analyses. If more than one measurement is taken during the visit window, the value taken on the scheduled visit will be utilized or if no scheduled visit was done, the first (earliest) measurement in the visit window will be used. If more than one measurement is taken on the same day, the assessment closest to the start of the dose will be used for on treatment values and the last measurement on the day will be used for post-treatment values. For worst overall post-baseline analyses, all assessments including those obtained from unscheduled visits will be included.

Table 7. Scheduled Study Visits

Study Visit	Study Day	Notes
Baseline	Day -1 or Day 1	Except where indicated, last measurement prior to the first dose of test article. Screening assessments are to be taken within 24 hours prior to the first dose of test article. If no test article is taken, the date and time of randomization is used in place of the first dose of test article.
On Treatment (note: analysis visit will be each Study Day)	Day 1, Day 2, Day 3, Day 7, Day 10	The Day 3 visit is to occur within 46 to 72 hours after the first dose of study drug and thus, may occur on Study Day 4. A Day 10 visit is will be conducted for subjects with treatment extending beyond 9 days, unless this visit coincides with the EOT Visit.
EOT		Within 2 days following the last dose of test article

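### When the Day 3 early-response visit falls on calendar Day 4, the plan holds the Day 3 odd-numbered dose to it and so conflicts with its own dosing schedule

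*Protocol*

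**What the plan says.** **The hold.** Protocol Section 8, footnote aa, has subjects instructed "not to take the odd numbered dose on Day 3 until they return to the site for the Day 3 visit". Section 14.3.1.1 adds that "Dose 1 and the odd numbered doses on Days 2 and 3 should be taken at the site".

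**The visit.** Section 14.1 places the ECR assessment at the Day 3 visit and says that it "must be conducted between 48 to 72 hours after the first dose of test article". SAP Section 5.2.1 widens the analysis window to 46 to under 73 hours. Study days are calendar days (Protocol Section 8, footnote b). SAP Table 7 (Section 8.6) draws the consequence: the visit is to fall "46 to 72 hours after the first dose of study drug and thus, may occur on Study Day 4".

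**The dosing schedule.** Protocol Section 15.1 gives omadacycline every 24 hours. Section 14.3.1.1 says: "Starting on Day 2, test article will be taken twice daily, with approximately 12 hours (at least 8 hours) separating each dose". Protocol Table 1 assigns an odd and an even dose to Day 3 and to every later day. The odd doses carry all the active omadacycline, and the even doses are placebo in that arm. Linezolid is active in both. The section headed "Permitted Dose Adjustments and Interruptions of Test Article" (14.3.2) contains one word, *None*. The only dose with a written rule for skipping is Dose 2 (Section 14.3.1.1, Table 1 footnote b, SAP Section 9.3).

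**The concern.** Each instruction is reasonable alone. Together they leave one foreseen case unresolved. If the visit is on Day 4, obeying footnote aa means that no odd-numbered dose is taken on Day 3, contrary to the schedule. A site must then choose between the hold and the schedule, and different sites may choose differently.

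The timing makes this matter. The held dose is the one due around the primary measurement, and it contains active drug for one arm's whole day but only part of the other's. A scheduling rule could therefore produce a difference in exposure between arms just before ECR is measured.

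**Working it through.** **Background figure.** The plan gives no figure for this point. Its sample size, used in step 4, reproduces. By the Farrington-Manning method with 79% in both arms, margin 10%, 90% power and one-sided 0.025, the restricted estimates are 0.7316 and 0.8316. Then n per arm = [(1.960 × 0.580 + 1.282 × 0.576) / 0.10]², about 351.5. That rounds up to 352 per arm, or 704 in total, as stated.

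**Step 1: where the window falls.** Let the first dose be at clock hour T on Day 1. The 48 to 72 hour window runs from T on Day 3 to T on Day 4, so 24 − T hours lie on Day 3 and T hours on Day 4.
- T = 10:00: 14 hours on Day 3, 10 on Day 4.
- T = 16:00: 8 and 16.
- T = 20:00: 4 and 20.

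Part of the window always lies on Day 3, but less of it after a late first dose. The SAP's 46-hour opening adds 2 hours on Day 3.

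**Step 2: gap between active omadacycline doses (Dose 3 to Dose 5) if the hold is obeyed.** Let c2 be the clock time of the Day 2 odd dose and cv that of the ECR visit.
- Visit on Day 3: gap = 24 + (cv − c2).
- Visit on Day 4: gap = 48 + (cv − c2).

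The clock times below are assumptions.

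| Dose 1 | Day 2 odd dose | ECR visit | Hours after Dose 1 | Gap (h) |
|---|---|---|---|---|
| 10:00 | 10:00 | Day 3, 10:00 | 48 | 24 |
| 15:00 | 09:00 | Day 3, 15:00 | 48 | 30 |
| 20:00 | 20:00 | Day 4, 09:00 | 61 | 37 |
| 20:00 | 09:00 | Day 4, 09:00 | 61 | 48 |
| 16:00 | 16:00 | Day 4, 16:00 | 72 | 48 |

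The first row shows no conflict. In the last three, no odd dose is taken on calendar Day 3. The fourth row is a first-day pattern that the protocol provides for: Dose 2 would have to be no earlier than 04:00 (8 hours after Dose 1) and no later than 01:00 (8 hours before Dose 3), so it is skipped.

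**Step 3: comparison of arms, fourth row.** Dose 4 is at about 21:00 on Day 2.
- If the Day 3 even dose is taken at about 21:00, the longest linezolid gap is 24 hours, 12 more than its 12-hour interval. The omadacycline gap of 48 hours is 24 more than its 24-hour interval.
- If the even dose also waits for the visit, the linezolid gap is 36 hours (21:00 on Day 2 to 09:00 on Day 4), also 24 more than its interval.

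The delay is therefore unequal under one reading and similar under the other. The documents do not say which applies.

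**Step 4: possible size (illustration only).**
- With the half-life of about 18 hours (Protocol Section 15.3) and simple exponential decay, 0.5^(24/18) = 40% of a dose remains at 24 hours and 0.5^(48/18) = 16% at 48 hours.
- If the true omadacycline ECR rate were 1, 2 or 3 points lower across the whole arm, power at 704 would fall from 90% to 83%, 73% or 60%. The arm-wide loss is the fraction affected times the loss among them. One point would need, for example, 10% of subjects each with a 10-point lower chance of response. The documents support no particular value.

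**Step 5: would compliance show it?** A 7-day omadacycline course has 3 + 3 + 5 × 2 = 16 active tablets. If one 300 mg dose were omitted, 14/16 = 87.5% would remain, above the 80% threshold for the clinically evaluable populations (SAP Section 6.1.5.5).

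**The case against.** The strongest reply is that the instructions can be followed together. Dose 1 is given at the site, so the 48-hour mark is a clock time at which that site was working on Day 1. A Day 3 visit then satisfies the hold, the window and the schedule. Section 14.3.1.1 also asks sites to think about procedures and fasting when timing these visits. This stands, and it makes the conflict conditional. It does not remove it, because the SAP expects some visits on Day 4.

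Other points stand in part:
- SAP Table 7 concerns assigning data to visits and is not a dosing instruction. A Day 3 dosing visit with a later lesion measurement is not excluded, since SAP Section 5.2.1 uses the latest measurement in the window. No passage tells sites to do this.
- The hold is worded as *should*, and Section 16.1.1 and footnote n foresee a dose taken before arrival. They do so only to set vital-sign timing and do not lift the hold.
- Moving a dose by hours is not clearly an interruption under Section 14.3.2, so *None* sits poorly with the hold without being plainly breached.

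Stronger readings are tempting but unsupported. A reader might infer that the dose is dropped; the text does not say whether it is moved or omitted. A reader might infer that omadacycline subjects always lose all of Day 3's active drug and linezolid subjects half; that holds only if the even dose is not also held. A reader might infer that afternoon first doses leave almost no clinic time on Day 3. Yet Section 16.1.1 calls for vital signs 3 hours after Dose 1, so a site dosing at 16:00 should be working until about 19:00.

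**Conclusion.** The point holds in conditional form. When the ECR visit falls on calendar Day 4, obeying footnote aa and Section 14.3.1.1 leaves no odd-numbered dose on Day 3. That conflicts with omadacycline every 24 hours, twice-daily dosing from Day 2 and Table 1. It is likelier after a first dose late in the day. With assumed clock times the gap between active omadacycline doses can reach about 48 hours just before the primary measurement, and the delay can be unequal between arms, depending on how the even dose is handled.

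A reader might go further and infer a biased primary result. The documents do not support that: they give no frequency of Day 4 visits and no effect of a delay on ECR. Any unequal delay would mainly work against omadacycline, so the likelier cost is power rather than a false claim of non-inferiority. This is a contradiction worth removing, not evidence against the endpoint.

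**What to change.** Reconcile Protocol Section 8 (footnote aa), Section 14.3.1.1 with Table 1, Section 14.3.2, Section 15.1 and SAP Table 7, so that all agree on what happens to the Day 3 odd and even doses when the ECR visit falls on Day 4. Which dosing instruction applies is for the sponsor to decide. The cost is a short protocol clarification with matching SAP wording.

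Optionally, add one descriptive SAP table by arm: the number of subjects whose ECR visit was on Day 4, and the time from last active dose to the ECR lesion measurement. Protocol Section 19.2 says that dates and times of all doses are recorded, and Section 15.4 refers to subject diaries. If those times reach the database for all subjects, and not only for those giving PK samples, no new data collection is needed.
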